6.3 PRO Endpoint

Not Applicable.

7. Analysis Subsets

7.1 Full Analysis Set

The full analysis set includes all subjects who received blinatumomab.

7.2 Safety Analysis Set

Safety analysis set is same as the full analysis set.

7.3 Responder Analysis Set

The responder analysis set includes all subjects who had CR or PR within 12 weeks after starting blinatumomab.

7.4 DLT Analysis Set

DLT analysis set includes all subjects who are DLT-evaluable.

7.5 Pharmacokinetic Analysis Set

The pharmacokinetic analysis set for blinatumomab includes all subjects who received any infusion of blinatumomab or pembrolizumab and have at least 1 pharmacokinetic sample collected.

7.6 Pharmacodynamic Analysis Set

The cytokine analysis set includes all subjects who receive any infusion of blinatumomab and have at least 1 **pharmacodynamic** sample collected.

For other biomarker analysis set include all subjects who received blinatumomab and pembrolizumab and have at least one biomarker sample collected.

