6.2.2.2.1 Dose modification of Pembrolizumab if Blinatumomab has been interrupted

If toxicities due to blinatumomab do not resolve to grade ≤ 1 within 7 days of treatment interruption and supportive care as outlined, pembrolizumab will also be interrupted until both may be resumed per protocol.

The first dose of pembrolizumab must be delayed if blinatumomab is interrupted during the step dose period per protocol (see [Table 6-1](#)). The first dose of pembrolizumab can only be given after the blinatumomab target dose is reached (+ 4 days); also, before adding pembrolizumab, there should be no blinatumomab dose interruption due to adverse events, no $>$ grade 1 CRS and/or neurologic events.

6.2.2.2.2 Dose Modification and Toxicity Management for Immune-related Adverse Events Associated With Pembrolizumab

Adverse events associated with pembrolizumab exposure may represent an immune-related response. These immune-related adverse events (irAEs) may occur shortly after the first dose or several months after the last dose of pembrolizumab treatment and may affect more than one body system simultaneously. Therefore, early recognition and initiation of treatment is critical to reduce complications. Based on existing clinical study data, most irAEs were reversible and could be managed with interruptions of pembrolizumab, administration of corticosteroids, and/or other supportive care. For suspected irAEs ensure adequate evaluation to confirm etiology or exclude other causes. Additional procedures or tests such as bronchoscopy, endoscopy, skin biopsy may be included as part of the evaluation. Dose modification and toxicity management guidelines for irAEs associated with pembrolizumab are provided in [Table 6-3](#).

Table 6-3. Dose Modification and Toxicity Management Guidelines for Immune-related Adverse Events Associated With Pembrolizumab

General instructions:				

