7.5 Biomarker Development

7.5.1 Immune Panel by Flow Cytometry

For subjects on blinatumomab, this assay will be used to monitor changes in lymphocytes (B-cell and T-cell populations) and leukocyte populations (leukocytes, lymphocytes, monocytes, and granulocytes) in peripheral blood. The rationale for an aggressive sample collection in the treatment period is to better understand the mechanism of action of the T cell response with the addition of pembrolizumab to blinatumomab, as well as potential drug resistance mechanisms.

The collection schedule is extensive to ensure adequate data is collected to better understand the mechanism of action of the T cell response elicited by the dual agent therapy, association with clinical response, and adverse events. In cohort Ia, samples will be collected days 1, 2, 3, 8, 10, 22, 43 and 64. In cohorts IIa and IIIa, samples will be collected days 1, 2, 3, 8, 15, 16, 19, 20, 26, 33, 40, 61, and 64. All samples will be collected in the first (induction) cycle of blinatumomab only. Immune panel samples must be drawn after dexamethasone premedication but no more than 15 minutes before initiation of blinatumomab therapy.

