10.1.2.4 Pharmacodynamic Analysis Set

The pharmacodynamic analysis set includes all subjects who receive any infusion of blinatumomab and have at least 1 pharmacodynamic sample collected.

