10.6.12 Pharmacodynamic Analysis

Blood samples for biomarker analysis will be taken as described in the Schedule of Assessment of protocol. The cytokine levels over time will be analyzed with summary statistics by treatment period and treatment cohort. The changes in Lymphocytes (B-cell, T-cell populations, NK cells), leukocyte populations (leukocytes, lymphocytes, monocytes, and granulocytes) and Tumor PD-L1 expression over time will be summarized with descriptive statistics by treatment period and treatment cohort. Other analysis may be performed as appropriate. There will be a separate biomarker SSAP developed with a molecular scientist.

Merck biomarker lead will define analysis related to pembrolizumab and PD-L1.

Analyses will be based on Pharmacodynamic Analysis Set.

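### SAP 7.6 limits the immune-panel and tumor PD-L1 analyses to subjects who received both drugs, while Protocol 10.1.2.4 asks only for blinatumomab and one sample, and SAP 11 does not declare the change

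*SAP*

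**What the plan says.** Protocol 10.1.2.4 defines a single set: "The pharmacodynamic analysis set includes all subjects who receive any infusion of blinatumomab and have at least 1 pharmacodynamic sample collected".

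SAP 7.6 splits it in two. For cytokines it keeps the protocol rule: "The cytokine analysis set includes all subjects who receive any infusion of blinatumomab and have at least 1" pharmacodynamic sample. For the rest it adds a second drug: "For other biomarker analysis set include all subjects who received blinatumomab and pembrolizumab and have at least one biomarker sample collected".

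SAP 10.6.12 summarises "The changes in Lymphocytes (B-cell, T-cell populations, NK cells), leukocyte populations (leukocytes, lymphocytes, monocytes, and granulocytes) and Tumor PD-L1 expression over time" descriptively by treatment period and cohort, and closes with "Analyses will be based on Pharmacodynamic Analysis Set". The lymphocyte and leukocyte populations are what Protocol 7.5.1 calls the immune panel.

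On starting pembrolizumab, Protocol 6.2.2.2.1 says that "before adding pembrolizumab, there should be no blinatumomab dose interruption due to adverse events", and also that there should be no CRS or neurologic event above grade 1. The blinatumomab target dose must already have been reached.

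**The concern.** The SAP drops subjects whom the protocol includes, and it drops them according to something that happens after treatment begins. Whether a subject ever receives pembrolizumab depends partly on how the first two to three weeks of blinatumomab were tolerated. Protocol 7.5.1 gives the purpose of the immune-panel schedule as understanding the T-cell response to the two agents together with its "association with clinical response, and adverse events". A subject stopped early for toxicity bears directly on the adverse-event part of that aim, and is the kind of subject the SAP set can remove.

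The rule also makes two related summaries describe different groups. The same early-stopping subject would appear in the cytokine tables and be missing from the cell-population tables.

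**Working it through.** The plan states no figure for this point, so there is nothing to reproduce. The check compares the texts, counts sampling days and illustrates the scale.

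**1. Is the wording deliberate?** The pharmacokinetic set in SAP 7.5, immediately before, accepts blinatumomab or pembrolizumab. SAP 7.6 says and. Read literally, both drugs are required.

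**2. Is it declared?** SAP 11 covers the decision not to run Part 2, duration of response and PFS. It mentions no analysis set. The SAP was written to protocol amendment 5; the rationale for amendment 6 lists no change to the pharmacodynamic set.

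**3. Which outputs does it reach?**
- Immune panel and tumor PD-L1: affected (SAP 10.6.12 with 7.6).
- Cytokines: not affected (own definition in SAP 7.6).
- MRD: not affected (full analysis set, SAP 10.5).
- DLT and efficacy: not affected (DLT set, full analysis set and responder set).

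**4. Can a subject fail to reach pembrolizumab for toxicity?** Yes. Protocol Table 6-1 permanently discontinues blinatumomab for grade 4 CRS, for grade 4 neurologic events, and for an initial grade 3 neurologic event at 9 µg/day. A subject stopped this way before the target dose cannot meet the condition for a first pembrolizumab dose.

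**5. Sampling days before planned pembrolizumab (Protocol 7.5.1).**
- Cohort Ia, pembrolizumab on day 15. The schedule is: "In cohort Ia, samples will be collected days 1, 2, 3, 8, 10, 22, 43 and 64". Days 1, 2, 3, 8 and 10 come first: 5 of 8.
- Cohorts IIa/IIIa, pembrolizumab on day 19. Of days 1, 2, 3, 8, 15, 16, 19, 20, 26, 33, 40, 61 and 64, the first six come before day 19: 6 of 13.

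For cohorts IIa/IIIa, the footnotes to Protocol Table 7-3 assign days 1 to 16 to blinatumomab exposure and days 19 to 64 to pembrolizumab exposure. Receipt of pembrolizumab is therefore irrelevant to what the early samples measure.

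**6. Scale, under an assumed rate.** Let p be the proportion who never receive pembrolizumab; the documents do not give it. With n subjects, the expected loss is n × p, and the chance of losing at least one is 1 − (1 − p)^n. For n = 6:

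| Assumed p | Expected loss, 6 × p | Chance of losing at least one |
|---|---|---|
| 5% | 0.3 | 1 − 0.95^6 = 26% |
| 10% | 0.6 | 1 − 0.90^6 = 47% |
| 20% | 1.2 | 1 − 0.80^6 = 74% |

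For a cohort expanded to 10, the expected loss is 0.5, 1.0 or 2.0 subjects. With Part 2 not proceeding, these small cohorts are all there is: one subject is 1/6 = 17% or 1/10 = 10% of a cohort.

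**The case against.** The best defence is that the trial studies a combination. Protocol 7.5.1 speaks of the response to dual-agent therapy, and Appendix H frames its hypothesis around both drugs. A both-drugs set suits that question. The endpoints are also exploratory and descriptive, and SAP 10.6.12 announces a separate biomarker plan that is not among the documents. This supports a both-drugs subset as an additional view. It does not justify silently replacing the protocol's set, and nothing says that the later plan will restore it.

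Several stronger readings are tempting but not supported:

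- **Any early adverse event excludes the subject.** It does not. Protocol 6.2.2.2.1 speaks of delaying the first pembrolizumab dose, and Table 6-1 allows restart after many grade 3 events. A subject who gets pembrolizumab late stays in the set with every sample, early ones included.
- **Exclusion will be common.** No document gives a frequency. Protocol 2.4 cites 21.7% grade 3 or higher neurologic events with step dosing in the earlier phase 2 monotherapy study (Protocol 2.1 gives 26.1%), but neither figure says how many subjects would never start pembrolizumab. Early progression is no firmer a basis, since the first scheduled disease assessment is on day 64.
- **All non-cytokine biomarkers are affected.** MRD is not. For PD-L1 the practical loss is small: the biopsies are optional and the second is taken at 10 weeks, so an early-stopping subject would usually contribute a baseline value at most.
- **The response rate is inflated.** ORR is estimated on the full analysis set (SAP 10.5), and no planned output reports a response rate in the biomarker set.

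**Conclusion.** The point holds as an undeclared difference between the SAP and the protocol in the analysis set for the immune panel and tumor PD-L1. The SAP definition conditions on a post-baseline outcome tied to early tolerability, and it discards valid pre-pembrolizumab samples from subjects who never start the second drug. It can therefore selectively remove early-toxicity subjects from summaries meant to inform the link with adverse events. How many subjects this concerns is unknown; the 26% to 74% range rests wholly on assumed rates of 5% to 20% and on independence between subjects. The consequence is confined to exploratory, descriptive output. It is worth correcting because the correction is nearly free, not because any main conclusion of the trial depends on it.

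**What to change.** In SAP 7.6, replace the second definition with that of Protocol 10.1.2.4, so that one set (any blinatumomab infusion and at least one pharmacodynamic sample) serves cytokines, immune panel and PD-L1 alike. Where a question concerns the effect of adding pembrolizumab, restrict by sample, using those taken after the first pembrolizumab dose, and leave the subject in the set. If a both-drugs subset is also wanted, present it as supplementary and declare it with its reason in SAP 11. Report how many subjects with immune-panel samples never received pembrolizumab.

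The cost is one sentence in SAP 7.6, plus an entry in SAP 11 if the subset is kept. No extra samples, visits or subjects are needed.

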7.7 Interim Analyses Set(s)

Interim analysis set will include all subjects at the interim analysis.

8. Interim Analysis and Early Stopping Guidelines

8.1 Interim Analyses

DRT will conduct evaluations of efficacy for ORR by the Lugano Classification (Cheson et al, 2014) during the first 12 weeks since starting blinatumomab and safety for DLT rate to assess if the threshold for early trial termination has been reached.

Table 2 shows the efficacy stopping rules using a Bayesian approach to potentially terminate the study if the posterior probability that ORR is less than 50% is $> 80\%$. The stopping boundaries assume a prior beta distribution (1, 1). The operating characteristics in Table 3 provide the probability of stopping the trial early for given hypothetical true ORR.

Table 2. Efficacy Stopping Boundary With Batch Size of 10 Subjects, Posterior Probability of 80% and ORR of 50%

Number of evaluable subjects	Stop study if observing these many responders
10	≤ 3
20	≤ 8
30	≤ 12
40	Always stop

Table 3. Operating Characteristics With Batch Size of 10 Subjects

True ORR	Prob of Stopping Early	Average Sample Size
0.40	70%	23
0.45	52%	27
0.50	34%	32
0.55	19%	19
0.60	9%	38

Table 4 shows the safety stopping rules using a Bayesian approach to terminate the study if the posterior probability that the DLT rate is greater than 25% is > 90%. The stopping boundaries assume a prior beta distribution (0.50, 1.50). The evaluations could occur more frequently if necessary, to address emerging safety concerns. The operating characteristics in Table 5 provide the probability of stopping the trial early for given hypothetical true DLT rates.

Table 4. Safety Stopping Boundary With Batch Size of 10 Subjects, Posterior Probability of 90% and DLT Limit of 25%

Number of DLT evaluable subjects	Stop study if observing these many DLTs
10	≥ 5
20	≥ 8
30	≥ 11
40	Always stop

DLT = dose limiting toxicity

Table 5. Operating Characteristics With Batch Size of 10 Subjects

True DLT Rate	Prob. of Stopping Early	Average Sample Size
0.20	6%	38
0.25	17%	36
0.30	36%	32
0.35	57%	27
0.40	76%	22

DLT = dose limiting toxicity; prob = probability

8.2 Dose Level Review Team (DLRT) and Data Review Team (DRT)

DLRT:

The DLRT will review safety data from each cohort in part 1 to determine if the combination of blinatumomab and pembrolizumab is safe and tolerable as defined by DLT criteria and general clinical judgement, taking into account a general benefit risk assessment. Pharmacokinetic data may be reviewed, if available.

Based on the totality of the data, the DLRT may recommend to declare MTD, to escalate to the next dose level, to expand a cohort to a maximum of 10 subjects, if the collection of more data is deemed warranted, or to adjudicate the DLT criteria.

The DLRT will meet to review the safety data, when any of the following criteria are met:

- In 2 or more **out of 6 subjects, a DLT has been reported or in 3 or more out of 10** subjects, a DLT has been reported in a cohort
- 6 subjects are enrolled in a cohort and all subjects have completed the DLT observation period
- In the event that a cohort is expanded to 10, DLRT **will** also meet after all subjects have completed DLT observation period

The DLRT will consist of, at minimum, members from the Amgen study team including at least one clinician, one safety representative, members outside the Amgen study team including at least one representative of the Merck study team, and one investigator participating in the study who has recruited subjects into the cohort under review. A cohort may be expanded by DLRT recommendation in the case that the data suggests a change to the anticipated risk/benefit profile, warranting collection of further data at the blinatumomab target dose.

In part 2, DRT will meet after every set of 10 subjects who become DLT evaluable.

A DRT is a group, internal to Amgen but external to the product team, that reviews accumulating data from the ongoing clinical trial to evaluate overall benefit and

risk. The DRT includes a clinician, a safety physician, and a biostatistician.

Experts external to Amgen may be included if needed. Membership, procedures and meeting timing will be described in detail in the study DRT charter.

9. Data Screening and Acceptance

9.1 General Principles

The objective of the data screening is to assess the quantity, quality, and statistical characteristics of the data relative to the requirements of the planned analyses. The database will be subject to edit checks outlined in the data management plan by Amgen Clinical Data Management (CDM) department. Any outstanding data issues will be communicated to CDM for resolution before the database is locked.

9.2 Data Handling and Electronic Transfer of Data

The Amgen Global Study Operations-Data Management (GSO-DM) department will provide all data to be used in the planned analyses. This study will use the RAVE Clinical database.

An Analysis Dataset for PK Concentrations (ADPC) will be provided to the appropriate Clinical Pharmacology Modeling and Simulation CPMS representative from Global Biostatistical Sciences.

9.3 Handling of Missing and Incomplete Data

Subjects without tumor response assessments will be considered as non-responders. Otherwise, only non-missing data will be analyzed. No other missing value replacement procedure will be deployed for clinical data. The handling of incomplete and partial dates for adverse events and concomitant medications are described in [Appendix A](#). Handling of missing or incomplete data for exposure-response analysis will be described in the E-R supplemental SAP (SSAP) or associated documents to support population PK/PD dataset generation and E-R analysis.

9.4 Detection of Bias

If applicable, the methods to detect bias are described in the analyses of particular endpoints.

9.5 Outliers

Any suspected outliers will be investigated by the study team and will be included in the database unless determined to be an error or there is supporting evidence or explanation to justify the exclusion. Any outliers excluded from the analysis will be

discussed in the Clinical Study Report (CSR), including the reasons for exclusion and the impact of their exclusion on the study.

PK serum concentration data will be evaluated for outliers by visual inspection, and decisions to re-assay individual samples will be made in accordance with standard pharmacokinetic evaluation practice.

9.6 Distributional Characteristics

The statistical assumptions for analysis methods will be assessed. If the assumptions for the distributional characteristics are not met, these will be described, and further analyses may be carried out using data transformations or alternative analysis methods. The use of transformations or alternative analysis methods will be justified in the final study report.

9.7 Validation of Statistical Analyses

Programs will be developed and maintained; and output will be verified in accordance with current risk-based quality control procedures.

Tables, figures, and listings will be produced with validated standard macro programs where standard macros can produce the specified outputs.

The production environment for statistical analyses consists of Amgen-supported versions of statistical analysis software; for example, the SAS System version 9.4 or later.

10. Statistical Methods of Analysis

10.1 General Principles

The analysis will be performed by cohorts for part 1. The analyses for part 2 will combine subjects in part 2 and the cohort in part 1 with selected dose for part 2 unless specified otherwise. The analyses will be performed on the Full Analysis Set unless specified otherwise.

Continuous variables will be summarized by the non-missing sample size n , mean, standard deviation, median, first and third quartiles, minimum, and maximum.

Categorical variables will be summarized by the n and percentage in each category.

Time to event endpoints will be summarized with hazard ratios, Kaplan-Meier (KM) curves, KM proportions at select time points, KM quartiles (when estimable), the number of subjects with events, the number of subjects censored, and the pattern of censoring.

Point estimates for efficacy endpoints will be accompanied by 2-sided 95% confidence intervals including estimates of KM quartiles (Brookmeyer and Crowley, 1982), KM

proportions (Kalbfleisch and Prentice, 1980), and binomial proportions (Clopper and Pearson, 1934). Pharmacokinetics will be performed by noncompartmental analysis. Pharmacodynamic samples will be summarized by descriptive statistics.

Relationships among drug exposures and efficacy, safety, and biomarkers may be explored if the data are sufficient.

10.2 Subject Accountability

The number (and percent) of subjects who were screened, received blinatumomab and pembrolizumab and complete the study will be summarized. The number (and percent) of subjects who discontinue each treatment and the study and their reasons for discontinuation will be summarized.

10.3 Important Protocol Deviations

Categories for Important Protocol Deviations (IPDs) are defined by the study team before the first subject's visit and updated during the IPD reviews throughout the study prior to database lock. These definitions of IPD categories, sub-category codes, and descriptions will be used during the course of the study. Eligibility deviations are defined in the protocol.

10.4 Demographic and Baseline Characteristics

Demographic (ie, age, age group, sex, race, and ethnicity) and baseline disease characteristics will be summarized using descriptive statistics. If multiple races have been reported for a subject, the subject will be categorized as multiple races as well as by combination of races.

The baseline characteristics to be summarized include:

- Age
 - age group: < 65, 65-74, ≥ 75
 - age as continuous variable
- Sex: Male, Female
- Race
 - American Indian or Alaska Native
 - Asian
 - Black (or African American)
 - Native Hawaiian or other Pacific Islander
 - White
 - Other

- Geographic region
 - US/Canada
 - Asia
 - Europe
 - Rest of the world
- aalPI: Low (0), Low-Intermediate (1), High-Intermediate (2), High (3)
- Primary disease status: Relapsed, Refractory
- Prior HSCT: Yes, No
- Extranodal disease: Yes, No.
- Cell of Origin Determination: GCB, Non-GCB, ABC, Not done
- Bcl-2 rearrangement status: Normal, Rearranged, Overexpressed, Not Overexpressed, Not done
- Bcl-2 overexpression status: Normal, Rearranged, Overexpressed, Not Overexpressed, Not done
- Bcl-6 rearrangement: Normal, Rearranged, Overexpressed, Not Overexpressed, Not done.
- Bcl-6 overexpression: Normal, Rearranged, Overexpressed, Not Overexpressed, Not done.
- C-myc rearrangement status: Normal, Rearranged, Overexpressed, Not Overexpressed, Not done
- C-myc overexpression status: Normal, Rearranged, Overexpressed, Not Overexpressed, Not done
- Double hit: Yes, No (Yes is defined by both C-myc and Bcl-6 overexpression and rearrangement are Yes; otherwise No)
- Triple hit: Yes, No, (defined as 'Yes' if all of Bcl-2, Bcl-6 and C-myc rearrangement are 'Yes', else 'No'.)
- Double high expressor: Yes, No, (defined as 'Yes' if Two of Bcl-2, Bcl-6, C-myc overexpression are Yes', else 'No'.)
- Triple high expressor: Yes, No, (defined as 'Yes' if all of Bcl-2, Bcl-6, C-myc overexpression are Yes', else 'No'.)

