7.3.3 Medical History

The investigator or designee will collect a complete medical and surgical history that started 5 years prior to screening through the time of enrollment. Medical history will include information on the subject's concurrent medical conditions. Diffuse large B-cell lymphoma history must date back to the initial diagnosis.

In addition to the medical history noted above, all history related to the subject's diagnosis of DLBCL (eg, date of initial diagnosis, additional risk factors at diagnosis, cell-of-origin [COO] at any timepoint if available [immunohistochemistry pattern, GEP/other], BCL-2 fluorescence in situ hybridization (FISH): translocation,

immunohistochemistry expression levels], c-myc [FISH: translocation, immunohistochemistry expression levels]) will be recorded.

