7.3.10 Bone Marrow Biopsy

A bone marrow biopsy will be performed at screening. Bone marrow biopsy is only required to be repeated with response assessments in case of infiltration or unclear results at screening and in order to confirm a CR. Available results of routine samples will be taken up to 49 days prior to enrollment. Bone marrow biopsy is not required if positron emission tomography (PET) scan is negative in marrow and if not otherwise clinically necessary by investigator discretion.

7.3.11 Core or Incisional/Excisional Biopsy for Biomarker Analysis, MRD by NGS, Cell of Origin, and FISH Analysis (optional)

If as part of the standard institutional procedure, and subject signs the optional consent, a tumor affected lymph node or tissue sample for the diagnosis of relapsed/refractory DLBCL will be collected for subjects enrolled into the study. In addition, a second biopsy is to be collected only in subjects who consent to additional biopsies. Samples should be collected 10 weeks after starting blinatumomab. Sites will process all tissue samples as outlined in the laboratory manual. Submission of formalin-fixed paraffin embedded tumor tissue sample blocks are preferred; slides or fresh frozen tissue are acceptable. All tissue sample preparation guidelines and requirements will be outlined in the laboratory manual.

Tissue will be used for exploratory analyses which may include and not be limited to MRD and immunohistochemistry (IHC). In addition, cell of origin analysis may be performed to determine DLBCL subtypes, and FISH analysis may be performed to determine gene rearrangements associated with double/triple hit DLBCL, if this information is not reported in the CRF under Medical History (see Section 7.3.3).

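### SAP 10.4's double-hit rule conflicts with its own triple-hit rule and with protocol 7.3.11, and all four hit/expressor variables count undetermined subjects as No

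*SAP*

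**What the plan says.** SAP 10.4 lists four derived Yes/No variables among the baseline characteristics.

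- Double hit: "Yes is defined by both C-myc and Bcl-6 overexpression and rearrangement are Yes; otherwise No".
- Triple hit: "defined as 'Yes' if all of Bcl-2, Bcl-6 and C-myc rearrangement are 'Yes', else 'No".
- Double high expressor: "defined as 'Yes' if Two of Bcl-2, Bcl-6, C-myc overexpression are Yes", and No in every other case.
- Triple high expressor: Yes if all three genes are overexpressed, and No in every other case.

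The inputs are six items, rearrangement and overexpression for each of Bcl-2, Bcl-6 and C-myc. All six carry the same five codes, for example "C-myc rearrangement status: Normal, Rearranged, Overexpressed, Not Overexpressed, Not done" and "Bcl-2 rearrangement status: Normal, Rearranged, Overexpressed, Not Overexpressed, Not done". None of the derived variables has an unknown category.

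Protocol 7.3.11 says that "FISH analysis may be performed to determine gene rearrangements associated with double/triple hit DLBCL" if the information is not already in the medical history. It does not mention expression in that connection, and the tissue is collected under an optional consent. Protocol 7.3.3 gives "BCL-2 fluorescence in situ hybridization (FISH): translocation" as an example of the disease history to be recorded, together with c-myc.

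SAP 9.3 counts subjects without a tumor response assessment as non-responders. Otherwise it uses only observed data and rules out any other replacement of missing clinical values.

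**The concern.** Double hit and triple hit sit in adjacent bullets but rest on different definitions. One combines rearrangement with overexpression and leaves out Bcl-2. The other uses rearrangement only and includes Bcl-2. Overexpression already has two variables of its own, so the extra condition mixes two concepts that the SAP otherwise keeps apart.

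Separately, 'Not done' is an allowed input code and the testing is partly optional, yet the catch-all No absorbs subjects whose status nobody knows.

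At stake is the accuracy of a baseline description in a small, uncontrolled study. SAP Section 11 records that Part 2 will not go ahead, so the table will describe Part 1 cohorts of up to 6 subjects, or 10 if expanded. In a cohort of 6 or 10, one misclassified subject moves the printed percentage by 1/6 = 17 or 1/10 = 10 points.

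**Working it through.** The plan states no figure to reproduce. The check applies each rule to every combination of its inputs. The counts below are logical patterns, not patients, and say nothing about how often a pattern occurs. 'Rearranged' and 'Overexpressed' are taken as Yes.

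**1. Double hit against triple hit, all six items known.** There are 2^6 = 64 patterns. Triple hit fixes the three rearrangement items at Yes and leaves three expression items free: 2^3 = 8 patterns. Double hit is also Yes only where C-myc and Bcl-6 are both overexpressed, with Bcl-2 expression free: 2 patterns. So 8 − 2 = 6 of 8 are triple hit Yes and double hit No.

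**2. The role of Bcl-2.** Fix C-myc and Bcl-2 as rearranged and Bcl-6 as not rearranged. The three expression items can each be Yes, No or Not done: 3^3 = 27 patterns. The SAP rule gives No in 27 of 27, because it requires Bcl-6 rearrangement.

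**3. Against a rearrangement-only rule.** Take double hit as C-myc rearranged plus Bcl-2 or Bcl-6 rearranged. This comparator is an assumption, built from the triple-hit rule and protocol 7.3.11. With everything known it is Yes in 3 rearrangement patterns × 8 expression patterns = 24 of 64. The SAP rule is Yes in 4 (C-myc and Bcl-6 rearranged and overexpressed, both Bcl-2 items free). All 4 lie within the 24, so 24 − 4 = 20 of 24 are labelled No.

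**4. 'Not done' in double hit.** The rule has four inputs, giving 3^4 = 81 patterns. At least one is Not done in 81 − 2^4 = 65, and all 65 return No. The rule leaves status open only where no input is negative: 2^4 − 1 = 15. In the other 50, a known negative settles No correctly. Counted over all six items (× 9 for the two unused Bcl-2 items), this is 585 patterns, of which 135 are undetermined.

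**5. 'Not done' in the other three.** Each uses three inputs: 3^3 = 27 patterns, of which 27 − 2^3 = 19 contain a Not done.

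- Triple hit and triple high expressor: undetermined in 2^3 − 1 = 7 of 19; the other 12 are settled No.
- Double high expressor, reading two as at least two: two positives settle Yes (3 patterns) and two negatives settle No (3 patterns), leaving 19 − 6 = 13 undetermined.

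Every undetermined pattern in all four variables prints as No.

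**6. Coding.** The rules test for Yes, which is not one of the five codes. The mapping is easily guessed but is not written down.

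**The case against.** The strongest reply is that this is one row of a descriptive table. Double hit is not an eligibility criterion, an endpoint, an input to a stopping rule or a named subgroup in protocol 10.1.3, and no ORR or PFS analysis in SAP 10.5 uses it. The same table prints each of the six marker items with its own 'Not done' count, so a reader can see how much testing is missing. All of this stands and limits the importance of the point. It does not remove the error: the marker rows give marginal counts, from which joint status cannot be recovered.

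A second reply is that the wording may have meant overexpression or rearrangement. That reading would remove the clash in step 1, since a triple-hit subject would then be double hit. It still omits Bcl-2 and still sends untested subjects to No. It would also label a subject double hit on overexpression alone, which does not fit protocol 7.3.11.

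A third reply is that no document names the gene pairs that make a double hit. That is correct, so the comparator in step 3 is a proposal for the sponsor to confirm. The conflict in step 1 does not depend on it. The absence of Bcl-6 from protocol 7.3.3 adds little, because that list is only of examples.

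**Conclusion.** The point holds as a definitional error confined to the descriptive baseline table. On its literal text, the double-hit rule contradicts the adjacent triple-hit rule, departs from the rearrangement basis in protocol 7.3.11, and returns No for every subject with C-myc and Bcl-2 rearranged and Bcl-6 not rearranged. All four variables print undetermined subjects as No, against SAP 9.3. The number of subjects affected cannot be computed, because the documents give no marker frequencies and no testing rates.

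Three stronger readings are tempting and are not supported:

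- A reader might infer that every subject with C-myc and Bcl-2 rearranged is missed. Such a subject is Yes if Bcl-6 is also rearranged and both C-myc and Bcl-6 are overexpressed.
- A reader might infer that any 'Not done' produces a false No. A known negative often settles No correctly, and two overexpressed markers settle double high expressor as Yes whatever the third.
- A reader might infer that high-risk disease is understated and the response or PFS results distorted. The documents do not call double hit high-risk, and no efficacy analysis uses the variable.

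The correction is worth making before the baseline table is produced, but nothing in the trial's conclusions on DLTs or efficacy turns on it.

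**What to change.** Amend SAP 10.4 as follows.

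- **Double hit:** define it on rearrangement alone, as C-myc rearranged plus Bcl-2 or Bcl-6 rearranged. State the role of Bcl-2, and whether triple-hit subjects are also counted as double hit. Leave overexpression to the two high-expressor variables.
- **Missing tests:** in all four variables, keep Yes or No wherever the known results settle the status, and assign Unknown only where a 'Not done' test leaves it open. For the revised double hit, Yes needs C-myc and at least one partner rearranged. No needs C-myc not rearranged, or both partners not rearranged. Anything else is Unknown.
- **Reporting:** give percentages among subjects with determined status, and show the number unknown beside them.
- **Coding:** state that 'Rearranged' and 'Overexpressed' map to Yes for their respective items, and that two in the double high expressor rule means at least two, if that is intended.

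The cost is a few lines of SAP text and a change to one derivation program. No new data are needed, since all six items are already listed for summary.
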